3.3.2 Exclusion Criteria

- Diagnosis of tumor before the diagnosis of T2D
- Diagnosis of secondary diabetes due to other pathologies
- Diagnosis of secondary diabetes due to other medications
- Diagnosis of secondary diabetes due to surgical interventions

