3.6 Follow-up and Events of Interest

Patients included in the study will be followed from the date of diagnosis of T2D until the date of the last available visit.

During the follow-up, for all included patients, the year of onset of the first cancer occurring after the diagnosis of diabetes and the type of cancer will be recorded. From this information, it will be possible to calculate the time elapsed between the diagnosis of diabetes and the onset of the tumor (measured in years).

For patients who have developed cancer, the following will also be recorded:

- Cancer recurrence (year of recurrence onset)
- Diagnosis of a second cancer unrelated to the primary cancer (year of onset, type of cancer)

Cancer diagnosis will be identified through the extraction system from the Smart Digital Clinic electronic medical record (Meteda Srl), using relevant keywords in the cancer domain, identified in the medical history section. The keywords will include: metastasis, adenocarcinoma, carcinoma, neoplasm, secondary, sarcoma, cancer, adenoma, lymphoma, leukemia, glioma, glioblastoma, basal cell carcinoma, squamous cell carcinoma, melanoma, mesothelioma, chordoma, anaplastic, differentiated, undifferentiated, meningioma, multiple myeloma, small cell carcinoma, thymoma, craniopharyngioma, neuroendocrine, LH, NHL, K, GIST, HCC, and NET.

SCDU di Endocrinologia

AOU Maggiore della Carità, [name]
[contact] (Reparto); [contact]
[contact]

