3.7 Data Collection

For each patient, the following variables will be extracted from the Smart Digital Clinic electronic medical record extraction system, when possible:

- Gender and age;
- Smoking habit and alcohol consumption (units per day);
- Weight and body mass index (BMI) at the first (T0) and last visit (T1);
- Date of diagnosis of T2D;
- Date of the first visit;
- Treatment for T2D at T0 and T1;
- Levels of glycated hemoglobin (HbA1c) at T0 and T1, average HbA1c, and average fasting blood glucose;
- Creatinine clearance at T0 and T1;
- Liver enzymes at T0 and T1: alanine aminotransferase (ALT) and aspartate aminotransferase (AST);
- Lipid profile at T0 and T1: low-density lipoprotein (LDL-c) and triglycerides (TG);
- Complications of T2D;
- Treatment for the cancer;
- Family history of cancers.

The diagnosis of T2D is confirmed at diabetic centers or, in some cases, by general practitioners who refer patients to specialized diabetic centers. The accuracy of the diagnosis will be confirmed by cross-referencing with the Piedmont Diabetic Registry (PDR) and involving a second person to ensure precise assessment.

Glycated hemoglobin will be considered high if its values exceed or equal 8%, indicating glycemic decompensation, while it will be considered low if it presents values below 8%.

BMI categories will be divided into underweight (BMI <18.5 kg/m²), normal weight (BMI 18.5 – 25 kg/m²), and overweight (BMI >25 kg/m²).

Regarding the treatment of T2D, participants will be categorized and grouped for statistical purposes into the following classes:

- Dietary therapy;
- Metformin/Acarbose;
- Sulfonylurea;
- Metformin + GLP1/DPP4 inhibitors (DPP4i) or only GLP1 or only DPP4i;
- Metformin + SGLT2 inhibitors (SGLT2i) or only SGLT2i;
- Basal insulin + GLP1/DPP4i +/- Metformin;
- Basal insulin +/- Metformin +/- SGLT2i;
- Basal bolus insulin;
- Basal bolus insulin +/- Metformin +/- SGLT2i.

Furthermore, complications of metabolic pathology will be extracted from the dedicated section of the program, where they are systematically recorded and organized, and their diagnosis is conducted in accordance with appropriate guidelines. These complications will be divided into the following categories: vasculopathy, neuropathy, hypertension, heart disease, renal failure, and retinopathy.

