Finally, regarding cancer, treatment will be categorized into three classes: chemotherapy, surgery, and radiotherapy. Additionally, cancer types will be divided to ensure greater homogeneity among groups, including the nervous system, head and neck, thorax, gastrointestinal, gynecological, urinary tract, male genital system, skin, blood, breast, soft tissues, endocrine glands, and neuroendocrine cancers.

Such information will be collected at the diabetes diagnosis visit and the last visit before cancer onset for subjects experiencing the event, and at the last available visit for the remaining subjects.

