3.9 Statistical Analysis

Descriptive statistics will be calculated to summarize patient information.

Categorical variables will be reported as absolute frequencies and percentages, while numerical variables will be reported as mean and standard deviation or median (Q1-Q3) if not distributed according to a normal random variable according to the Shapiro-Wilk test and observation of the QQ plot.

SCDU di Endocrinologia

AOU Maggiore della Carità, [name]
[contact] (Reparto); [contact]
[contact]

Univariate and multivariate Cox proportional hazards regression models will be used to estimate hazard ratios (HRs) and corresponding 95% confidence intervals (95% CI) for the association between some risk factors, including particularly glycemic level, and cancer onset. The stepwise method will be used to select variables to include in the model. For this analysis, time to event will be calculated as the number of years between cancer onset and diabetes diagnosis for subjects who develop the cancer, and as the number of years between the last available visit and the date of diabetes diagnosis. The possibility of conducting an analysis separately for cancer type or considering specific cancer types based on the number of observed events will be evaluated. The same models will be used to estimate the association with the risk of recurrence, second cancer, or both in patients who have developed cancer. In this case, time to event will be calculated considering the difference in years between recurrence onset, second cancer, or last visit and the onset of the first cancer.

Linear regression models will be used to evaluate the relationship between variables measured at diagnosis and time to cancer onset. In case the assumptions of the linear model are not met (normality of residuals and homoscedasticity), the Spearman correlation coefficient will be calculated to measure the correlation between numerical variables and time to tumor onset, while the Mann-Whitney or Kruskall-Wallis tests will be used when variables measured at baseline are categorical.

The significance level will be set at 0.05, and all tests performed will be two-tailed. Finally, the analyses will be conducted using SAS software (version 9.4; SAS Institute, Cary, NC, USA).

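### With no lag after T2D diagnosis, tumours present but undiagnosed at that point count as incident cancers, and a consequence of cancer can be reported as a risk factor

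*Combined protocol and SAP*

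**What the plan says.** Under section 3.6 patients are "followed from the date of diagnosis of T2D until the date of the last available visit", and for cancers "the year of onset of the first cancer occurring after the diagnosis of diabetes and the type of cancer will be recorded". The T2D diagnosis is held more finely: section 3.7 lists "Date of diagnosis of T2D".

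The only criterion directed at existing cancer is in section 3.3.2: "Diagnosis of tumor before the diagnosis of T2D". The same section also removes diabetes secondary to other diseases.

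In section 3.9, "time to event will be calculated as the number of years between cancer onset and diabetes diagnosis for subjects who develop the cancer". No minimum interval is set. Section 3.9 also regresses time to cancer onset on variables measured at T2D diagnosis.

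Section 3.7 collects "Levels of glycated hemoglobin (HbA1c) at T0 and T1, average HbA1c, and average fasting blood glucose". The closing value in cases comes from "the last visit before cancer onset for subjects experiencing the event", again with no minimum gap. Section 3.9 names glycaemic level as the exposure of particular interest but does not say which HbA1c measure enters the model.

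**The concern.** A tumour can exist for some time before it is diagnosed. If it was already there when T2D was diagnosed, HbA1c and weight at that visit may partly result from the tumour. The plan counts such a tumour as an event occurring after exposure, so reverse causation would appear as a hazard ratio.

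The time-to-onset regression is exposed in the same way. Occult tumours sit at times near zero, so if they raised HbA1c or lowered weight they would directly produce a relation between those variables and earlier cancer.

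This matters because glycaemia drives the sample size in section 3.8, and section 4 intends the results to guide prevention.

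**Working it through.** **The plan's own figures.** The plan gives no figure for early cancers, so there is none to reproduce on this point. Its 779 events (section 3.8) serve below only as a scale. That count does not follow from the stated hazard ratio of 1.2. Schoenfeld's formula gives (1.960 + 0.842)² / (0.13 × 0.87 × ln(1.2)²) = 2,088, and 2,088 / (1 − 0.1²) = 2,109. The same formula gives 778.3 at a hazard ratio of 1.35. That is a separate matter and does not change this one.

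**1. Does any provision stop an undiagnosed tumour from counting?**
- The prior-tumour exclusion in 3.3.2 needs a diagnosis.
- The secondary-diabetes exclusion needs a recognised link.
- Sections 3.6 and 3.9 start the clock at T2D diagnosis.
- Sections 3.6 to 3.9 contain no lag, landmark, same-year rule or early-event sensitivity analysis.

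So nothing does.

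**2. Share of early cancers (assumption).** With steady incidence and mean follow-up M years, about 1/M of events fall in the first year: 1/15 = 7% to 1/10 = 10%, or 55 to 78 of 779. This is the ordinary first-year yield and not all of it need be occult at T2D diagnosis, so 2–3% is shown as well.

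**3. Hazard ratio under a true null.** Let s be the occult share of events. Assume 30% of occult cases have high HbA1c, against the 13% of section 3.8.

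p = (1 − s) × 0.13 + s × 0.30; HR ≈ [p/(1 − p)] / (0.13/0.87)

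| s | p | HR |
|---|---|---|
| 2% | 0.1334 | 1.03 |
| 3% | 0.1351 | 1.05 |
| 7% | 0.1419 | 1.11 |
| 10% | 0.1470 | 1.15 |

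If only half of the first-year cancers affect HbA1c, s falls to 3.5–5% and the HR to 1.05–1.08. With one third, s is 2.3–3.3% and the HR about 1.035–1.05. With none, p = 0.13 and the HR is 1.00.

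**4. False-positive rate.** With 779 events the Wald statistic shifts by √(779 × 0.99 × 0.1131) × ln(HR) = 9.34 × ln(HR). Two-sided rejection at a nominal 5% becomes about 7% at s = 3%, 16% at 7% and 27% at 10%.

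**5. Does a lag remove the bias?** Cox simulation, 2,000 runs per row: 5,600 patients, 13% with high HbA1c, 1% annual incidence unrelated to HbA1c, 8–20 years of follow-up, and occult tumours in 0.7% of low-HbA1c patients, all surfacing within one year.

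| Occult risk, high vs low HbA1c | Occult / events | HR, no lag (rejection) | HR, 1-year lag (rejection) |
|---|---|---|---|
| 1 | 39 / 763 | 0.990 (4.9%) | 0.994 (5.2%) |
| 2 | 44 / 769 | 1.047 (8.4%) | 1.000 (5.2%) |
| 3 | 50 / 772 | 1.103 (17.9%) | 0.995 (5.1%) |

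A ratio of 3 puts 0.39 / (0.39 + 0.87) = 31% of occult cases in the high group, close to the 30% in step 3. The lag works fully here because every simulated occult tumour surfaces within it; tumours silent for longer would remain.

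**6. Same-year cancers.** A stored year cannot show whether a cancer preceded or followed a T2D date in that year. Dropping same-year cancers is also not a 12-month lag: with diagnoses spread evenly over the year, half of the cancers in the first 12 months fall in the next calendar year.

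**The case against.** Several stronger readings are tempting, and the documents do not support them.

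- **Early tumours alone could produce the planned hazard ratio of 1.2.** The formula in step 3 needs s = 13% for that (p = 0.1521), above the 7–10% that steady incidence suggests, and it needs 30% high HbA1c in every one of those cancers. The documents give neither figure. The plan covers all tumour types, including skin and breast, and offers no basis for a uniform HbA1c shift.
- **Year-only recording is what lets occult tumours in.** It is not. Exact dates without a lag would admit them too.
- **Same-year cancers can never be ordered.** The exclusion in 3.3.2, the restriction in 3.6 to cancers after T2D, and the use in 3.7 of a last visit before onset all presuppose some ordering in the chart. The documents do not say the stored year is the only information used for eligibility. What is missing is a written rule.
- **The exposure is HbA1c at diagnosis.** Sections 3.7 and 3.9 leave the measure open. The figures above apply to a baseline value and do not carry over to the last or average HbA1c. For those, the route stays open throughout follow-up, because the last value in cases is taken just before cancer onset.

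It can also be said that the study aims to identify associations, so a lagged primary model is partly a preference. That stands: a pre-specified sensitivity analysis would meet the concern. What remains is that the plan as written counts undiagnosed baseline tumours as incident and has no analysis that would show whether they drive a result.

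**Conclusion.** The point holds. The missing lag is the main defect; year-only onset is secondary, because it leaves same-year eligibility without a rule and limits how precisely a lag can be applied.

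The bias cannot be sized from the documents. It rests on two assumed quantities, the share of occult tumours and their HbA1c. Across the ranges shown it runs from none, through a hazard ratio of about 1.03–1.05, to about 1.11–1.15, the last only if all first-year cancers behave as occult tumours with 30% high HbA1c. The effect on weight and on the time-to-onset regression follows the same logic and was not quantified.

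The plan should be changed, preferably before extraction, since date information not extracted then is harder to recover.

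**What to change.** Extract the month or full date of cancer diagnosis where recorded, and add to section 3.9:

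> A landmark Cox analysis starts risk time 12 months after T2D diagnosis (or at first visit if later) and removes from the risk set patients with cancer or censoring before that point. Where only the year of onset is known, an analysis starts all patients at 1 January of the second calendar year after the year of T2D diagnosis, which guarantees at least 12 months. Cancers in the same calendar year as T2D that cannot be ordered are excluded from the cohort, not kept as cancer-free. HbA1c and weight values used in this analysis are measured at or before the landmark. The time-to-onset regression is repeated without the early cancers. Lagged and unlagged results are reported together, and an HbA1c association that disappears with the lag is not reported as a risk factor.

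Whether the lagged model is primary or a pre-specified sensitivity analysis is the sponsor's choice.

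The cost is SAP wording, a few extra model runs, and date extraction where dates exist. With steady incidence and 10–15 years of mean follow-up, a 12-month lag loses about 7–10% of events. The calendar-year version starts 12–24 months after diagnosis, 18 on average, and loses 1.5/15 to 1.5/10, or 10–15%. If occult tumours come on top of steady incidence the loss is larger: in the last simulation row events fell from 772 to 665, or 14%. Keeping 779 events after a 10% loss would need 779 / 0.90 = 866 identified cases; after 15%, 779 / 0.85 = 917.

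### The cancer keyword list in section 3.6 omits 'tumor', the protocol's own synonym for the outcome, so a patient recorded only under that word would be analysed as cancer-free

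*Combined protocol and SAP*

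**What the plan says.** Section 3.6 identifies cancer diagnoses by extraction from the clinic's electronic record, "using relevant keywords in the cancer domain, identified in the medical history section". The list starts "The keywords will include: metastasis, adenocarcinoma, carcinoma, neoplasm, secondary, sarcoma, cancer, adenoma, lymphoma, leukemia" and ends "meningioma, multiple myeloma, small cell carcinoma, thymoma, craniopharyngioma, neuroendocrine, LH, NHL, K, GIST, HCC, and NET". It holds 32 terms, from general words ('cancer', 'neoplasm', 'carcinoma') down to abbreviations and a single letter ('K').

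The event is defined in the same section: "the year of onset of the first cancer occurring after the diagnosis of diabetes and the type of cancer will be recorded". The sentence that follows calls the same event a tumor when it defines the elapsed time from diabetes diagnosis. Section 3.9 does so again, where a rank correlation is planned "to measure the correlation between numerical variables and time to tumor onset". Section 3.3.2 excludes patients with "Diagnosis of tumor before the diagnosis of T2D".

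The only verification described is for diabetes. Section 3.7 says of the type 2 diabetes (T2D) diagnosis: "The accuracy of the diagnosis will be confirmed by cross-referencing with the Piedmont Diabetic Registry (PDR) and involving a second person". No counterpart is given for cancer.

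**The concern.** The keyword search is the only case-finding rule stated for the primary outcome. The authors use 'tumor' interchangeably with 'cancer', so they can hardly assume that clinicians' notes avoid the word. An entry such as 'breast tumor' or 'tumor of the colon' contains none of the listed terms. The list carries the abbreviation GIST, but the spelled-out form, gastrointestinal stromal tumor, would not be found either.

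A case missed in this way does not drop out of the analysis. It stays in the cohort as a cancer-free patient. What is at stake is therefore misclassification of the outcome, and of the covariates whose timing depends on the outcome, as well as a smaller number of identified events.

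**Working it through.** **1. The list against the word.** Each of the 32 terms in section 3.6 was compared with 'tumor', 'tumour' and the Italian 'tumore', in both directions. Terms containing the letters 'tum': 0 of 32. Terms that are themselves contained in one of the three words: 0 of 32. So neither whole-word nor substring matching on a listed term would retrieve an entry through the word 'tumor'.

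**2. Where the protocol uses the word.**

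| Place | Use | Term in the keyword list? |
|---|---|---|
| 3.6, event recorded | cancer | yes |
| 3.6, elapsed time | tumor | no |
| 3.9, time-to-onset analysis | tumor | no |
| 3.3.2, exclusion | tumor | no |

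**3. What happens to a patient whose history has 'tumor' and none of the 32 terms.**
- Under 3.6 no cancer is identified.
- Under 3.6 and 3.9 the patient's time runs to the last available visit and is censored there. Follow-up after the unrecognised cancer is counted as cancer-free.
- The end of 3.7 takes covariates from the last visit before cancer onset for cases and from the last available visit for everyone else. This patient's T1 weight, HbA1c, treatment and laboratory values therefore come from the last available visit, which may fall after the cancer.
- The patient is also absent from the time-to-onset analysis and from the recurrence and second-cancer analyses, which are confined to patients with an identified cancer.

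**4. Size.** The documents do not say what share of cancers is recorded under this word alone, so the loss cannot be calculated. A range can be shown by assumption.

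The only planned figure involved is the requirement of 779 cases in 3.8. It was not reproduced from its stated inputs (two-sided alpha 0.05, power 80%, prevalence 0.13, HR 1.2, correlation 0.1 read as R² = 0.01). The usual formula for a binary covariate in a Cox model, with normal quantiles 1.960 and 0.842, gives

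D = (1.960 + 0.842)² / [0.13 × 0.87 × (ln 1.2)² × 0.99] ≈ 2,109.

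That discrepancy is a separate matter. Here 779 serves only as the stated target, and the inflation factor below does not depend on it.

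Section 3.8 asks for 779 cases to be *identified*. If a share m of true cancers is missed, the number of true cases needed is 779 / (1 − m), rounded up:

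| Assumed share missed, m | Calculation | True cases needed | Extra over 779 |
|---|---|---|---|
| 2% | 779 / 0.98 = 794.9 | 795 | 16 |
| 5% | 779 / 0.95 = 820.0 | 820 | 41 |
| 10% | 779 / 0.90 = 865.6 | 866 | 87 |

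**The case against.** The strongest reply has three parts.

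First, the list is introduced as what the keywords will include, so it may not be exhaustive. The clinic is Italian, so the English terms may translate a query that already contains the equivalent word. This stands as a reason to word the point conditionally. It does not remove it: the list is detailed down to rare entities and single abbreviations, it contains redundant terms (several already contain 'carcinoma'), and no other search rule is given. It reads as a working list. If the real query is longer, the plan need only print it.

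Second, one entry worded 'tumor' does not lose a patient. The patient is lost only if none of the 32 terms, including 'cancer', 'neoplasm', 'carcinoma' and 'K', appears anywhere in the searched history. That is correct, and it may make the affected share small.

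Third, the event itself is worded as cancer, which is listed. That is also correct, but it does not help a record that uses only the other word.

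A reader might go further in three ways that the documents do not support.
- *Prior tumors escape the exclusion.* Section 3.3.2 gives no screening method, and nothing says that the keyword search is used to apply it. The plan is silent here, and an error cannot be inferred from that silence.
- *A later entry such as 'metastasis' is taken as a first cancer with a false onset year.* This would need retrieved entries to go uninterpreted. Sections 3.6 and 3.7 require onset year, cancer type, treatment and whether a second cancer is unrelated to the first. A bare keyword hit supplies none of these, so someone has to read the entry.
- *A stated number of the 779 cases, and a stated amount of power, is lost.* The 779 is already a count of identified cases, so subtracting missed cases from it is the wrong operation. No share is documented from which a power loss could be derived.

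**Conclusion.** The point holds in conditional form. As written, the sole case-finding rule for the primary outcome cannot retrieve a cancer recorded only as a tumor, and no second source or check for cancer is described. Such a patient would be censored as cancer-free, with T1 covariates taken at the wrong visit for a case.

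This rests on two assumptions: that the printed list is the list applied, and that some patients' histories contain the word and none of the 32 terms. The size is unknown. The figures of 795, 820 and 866 true cases illustrate assumed losses of 2%, 5% and 10% and are not estimates. Nothing in the documents suggests that use of the word varies with HbA1c, so no particular bias in the glycemia hazard ratio is shown. The change is worth making because it is specific and nearly free, not because a large effect has been demonstrated.

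**What to change.** In section 3.6:

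- Add 'tumor/tumour' as a word stem, in the language of the record, to the keyword list. If the actual query already contains it, print the actual query.
- State that benign hits are resolved when the retrieved entries are read and assigned to a cancer group. The list already needs this step, since 'adenoma' and 'meningioma' will also bring in benign entries.
- State whether the same list is used to screen pre-diagnosis history for the exclusion in 3.3.2, or describe how that exclusion is screened.

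The cost is one more search stem, two sentences of text, and somewhat more entries to read, some of them benign. The analysis models do not change.

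### Section 3.6 identifies the first cancer by keywords that include a benign term (adenoma), and no available section requires a hit to be malignant

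*Combined protocol and SAP*

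**What the plan says.** Section 3.6 names the event: for every patient, "the year of onset of the first cancer occurring after the diagnosis of diabetes and the type of cancer will be recorded". It then gives the only stated route to it: "Cancer diagnosis will be identified through the extraction system from the Smart Digital Clinic electronic medical record", by keywords searched in the medical history section. The list opens with "metastasis, adenocarcinoma, carcinoma, neoplasm, secondary, sarcoma, cancer, adenoma, lymphoma, leukemia" and later contains "meningioma, multiple myeloma, small cell carcinoma, thymoma, craniopharyngioma, neuroendocrine". For patients who have had a first cancer, recurrence is also recorded, as is "Diagnosis of a second cancer unrelated to the primary cancer".

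Section 3.7 contains one verification step: "The accuracy of the diagnosis will be confirmed by cross-referencing with the Piedmont Diabetic Registry (PDR) and involving a second person". It stands in the paragraph on how T2D is diagnosed. The same section sorts cancers by site, from the nervous system through to "breast, soft tissues, endocrine glands, and neuroendocrine cancers", and treatment into chemotherapy, surgery and radiotherapy. Covariates are collected at the diabetes diagnosis visit and again at the "last visit before cancer onset for subjects experiencing the event, and at the last available visit for the remaining subjects".

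Section 3.9 measures time to event from diabetes diagnosis to cancer onset. Section 3.3.2 excludes patients with a tumour before T2D. Sections 3.6 and 3.9 use tumour and cancer interchangeably.

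**The concern.** Adenoma is a benign term. This is general clinical usage, not something the protocol states. A list that identifies cancer diagnoses and contains this term needs a rule that separates benign from malignant hits, and none is written in the available text. The population-defining diagnosis (T2D) has a written check, while the outcome has none.

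Because the event is the *first* cancer, one wrong entry does more than add a false case. It fixes the onset year used in the Cox models and in the time-to-onset analysis (secondary objective 3). It reclassifies a later true cancer as a second cancer (secondary objective 2). It may also change the visit from which a case's later covariates are taken.

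**Working it through.** **Plan's own figures.** The plan gives no share of hits that are benign, so there is no figure of that kind to reproduce. The nearest is the 779 cancer cases in section 3.8 (two-sided 0.05, 80% power, 13% with high HbA1c, hazard ratio 1.2, correlation 0.1). The standard Cox formula is

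D = (z_alpha + z_power)² / [p(1−p)(ln HR)²(1−R²)].

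Without the covariate term, D = (1.960 + 0.842)² / [0.13 × 0.87 × (ln 1.2)²] = 2,088. With R² = 0.01 (0.1 read as a correlation) it is 2,109; with R² = 0.10 it is 2,320. The 779 does not reproduce. That is a separate matter and no evidence for this point, but it leaves no sound power baseline from which to compute a loss here.

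**Could a benign hit pass each later step?** Take a resected adenoma first noted after T2D.

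1. Section 3.6, keyword: it matches.
2. Section 3.6, year and type: it has both.
3. Section 3.7, site group: the groups are by site, not behaviour, so it can fit endocrine glands or gastrointestinal.
4. Section 3.7, treatment: surgery is a listed class.
5. Section 3.7, verification: the check concerns T2D.

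Only the ordinary meaning of the word cancer, as understood by whoever reads the note, would stop it.

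**What follows if it is counted.**

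- The onset year is wrong in the Cox model and in the time-to-onset analysis.
- A later true cancer becomes a second cancer.
- The covariate visit for that case becomes the last one before the adenoma. Section 3.9 does not say whether the Cox model uses first-visit, last-visit or average HbA1c, so this matters only if last-visit or average values enter. The linear models for time to onset use variables measured at diagnosis, so there only the outcome is affected.

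**Effect on the hazard ratio.** Let f be the share of counted events that are false among patients without high HbA1c, and HR_false the hazard ratio of the false events. With the false-to-true ratio constant over time,

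HR_obs = (1 − f) × 1.20 + f × HR_false.

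The 1.20 is from section 3.8; f and HR_false are assumptions.

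False events unrelated to HbA1c (HR_false = 1.0):

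| f | calculation | HR_obs |
|---|---|---|
| 2% | 0.98 × 1.20 + 0.02 | 1.196 |
| 5% | 0.95 × 1.20 + 0.05 | 1.19 |
| 10% | 0.90 × 1.20 + 0.10 | 1.18 |
| 20% | 0.80 × 1.20 + 0.20 | 1.16 |
| 30% | 0.70 × 1.20 + 0.30 | 1.14 |

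False events related to HbA1c, at f = 20%:

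| HR_false | calculation | HR_obs |
|---|---|---|
| 0.8 | 0.96 + 0.16 | 1.12 |
| 1.0 | 0.96 + 0.20 | 1.16 |
| 1.2 | 0.96 + 0.24 | 1.20 |
| 1.5 | 0.96 + 0.30 | 1.26 |

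The calculation ignores true cancers displaced by an earlier benign event.

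**The case against.** The strongest reply is that the list is a search screen, not an event definition. Section 3.6 names the event separately as cancer. Several keywords (K, LH, secondary, differentiated) do not by themselves identify a tumour type or site, so hits cannot become events automatically. Someone must read the note to record type, year and treatment, and to separate a recurrence from an unrelated second cancer. A broad screen is ordinary practice, and a careful reader may well reject an adenoma. This stands in part: it makes miscounting less certain. It does not supply the missing rule, because the text says that diagnoses are identified by the search and gives the reader no criterion.

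Four stronger readings might be inferred, and the documents support none of them:

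- *The study will count benign tumours.* The text permits it; nothing shows that it will happen.
- *Listing meningioma and craniopharyngioma is an error.* These are usually benign, but the plan has a nervous system group and uses tumour alongside cancer, so counting them may be intended. For these two the gap is an unstated definition.
- *The hazard ratio will be pulled towards 1.* This holds only if false events are unrelated to HbA1c. If, for example, patients with high HbA1c are seen or imaged more often, the bias could go the other way.
- *A given amount of power is lost.* The false-event share is unknown and the plan's 80% does not follow from its stated inputs.

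The part between sections 3.1 and 3.3 was not available, so absence is claimed only for the text that was. Sections 3.6 and 3.7, where such a rule would belong, are present.

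**Conclusion.** The point holds as a gap in the definition of the primary event. As section 3.6 is worded, an adenoma can be entered as a first cancer and nothing written later would remove it. The documents do not show that this has happened or will happen.

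The effect may be negligible or moderate. At a 2% share of unrelated false events the hazard ratio barely moves (1.196). At 20 to 30% it falls to 1.16 to 1.14, which is material against a target of only 1.2. These shares are illustrations without an anchor in the documents, and the direction is open if false events depend on HbA1c. The wrong onset year and the relabelled second cancer follow for any miscounted patient who has them; the covariate-visit effect is conditional on the model. The change is worth making before extraction because it costs little and concerns the event on which the primary analysis rests.

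**What to change.** In section 3.6:

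1. State that keywords only flag candidate records.
2. Count an event only when the note documents a malignant tumour in the patient, with type or site and year, so that adenoma alone is never an event.
3. State before extraction whether meningioma, craniopharyngioma and other borderline tumours count.
4. Apply the same definition to second cancers and to the prior-tumour exclusion in section 3.3.2.

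Whoever already reads the notes for type, year and treatment can make this decision in the same pass, so no extra reader is needed. The cost is a few sentences of protocol text, slightly more abstraction work, and fewer counted events.
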